5.3.2. Safety Analyses

The safety analyses will be based on the Safety analysis set, unless otherwise specified.

5.3.2.1. Extent of Exposure

- Number of days of exposure to study drug will be calculated based on the formula: Duration of Exposure in Weeks = (Treatment stop date – Treatment start date)/7
- Duration will be summarized by treatment group. Each subject will contribute duration of exposure to the treatment taken.
- Participants who were randomized but not report a treatment start date will be categorised as having zero days of exposure.

A listing and summary table of exposure will be created.

The details of the planned displays are in programming specification document.

5.3.2.2. Adverse Events

AEs will be coded using the most recent version of the Medical Dictionary for Regulatory Activities (MedDRA).

A treatment emergent adverse event (TEAE) is defined as an event that has onset date on or after the first day of exposure to infusion treatment and on or before the last day of infusion treatment. Here the first day of exposure is defined as the first day of exposure to infusion treatment.

Treatment Adverse events (TAES) are summarised descriptively, whereas non-TEAEs are presented in listings. TAE data will be displayed in terms of the number of subjects with at least one event (N), percentage of subjects with at least one event (%) and the number of events (E).

Summaries of TAEs and of serious AEs will be presented as an overview including all AEs, serious AEs, AEs by severity, AEs by relation to treatment, action to AEs and treatment advised, and outcome of AEs.

Furthermore, summary tables based on system organ class and preferred terms are made for:

- All TAEs
- Serious AEs

Hope Biosciences Research Foundation HBPCOVID02

• AEs leading to withdrawal of study

Incidence and risk of AEs of special interest (includes serious or nonserious), including thromboembolic events, infections, and hypersensitivities will be summarized based on system organ class and preferred terms.

Individual adverse events will be listed.

The details of the planned displays are in programming specification document.

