Duration of administration	1 hour
Laboratory Samples.	Screening, Week 0, 6, and 26.

	Screening
Visits by Weeks	Week 0 _ Infusion 1
	Week 2 _ Infusion 2
	Week 6 _ Infusion 3
	Week 10 _ Infusion 4
	Week 14 _ Follow Up 1
	Week 20 _ Follow Up 2
	Week 26 – End of Study

“A randomized, double-blinded, single-center, phase 2 efficacy, and safety study of allogeneic HB-adMSCs for the treatment of patients with Chronic Post-COVID-19 Syndrome.”

Objectives

Primary Objectives

- To investigate the efficacy of intravenous infusions of HB-adMSCs (allogeneic) vs. Placebo in patients with Chronic Post-COVID-19 Syndrome as determined by improvements in individual symptom scores of Visual Analog Scale of Neurological Symptoms. (Time frame: Baseline to Week 26).
- To assess the safety of intravenous infusions of HB-adMSCs (allogeneic) vs. Placebo in patients with Chronic Post-COVID-19 Syndrome as determined by the incidence of adverse events or serious adverse events (Time frame: Baseline to Week 26).

Secondary Objectives

- To investigate the efficacy of intravenous infusions of HB-adMSCs (allogeneic) vs. Placebo in patients with Chronic Post-COVID-19 Syndrome as determined by improvements in individual symptom scores of Visual Analog Scale of Non-Neurological Symptoms. (Time frame: Baseline to Week 26).
- To evaluate the efficacy of intravenous infusions of HB-adMSCs (allogeneic) vs. Placebo in patients with Chronic Post-COVID-19 Syndrome as determined by changes in Fatigue Scale (Time frame: Baseline to Week 26).
- To assess the efficacy of intravenous infusions of HB-adMSCs (allogeneic) vs. Placebo in patients with Chronic Post-COVID-19 Syndrome as determined by changes in SF-36 Quality of life self-assessment. (Time frame: Baseline to Week 26).
- To identify the safety of intravenous infusions of HB-adMSCs vs. Placebo in patients with Chronic Post-COVID-19 Syndrome as determined by changes in Patient Health Questionnaire (PHQ-9).

Endpoints

Primary Endpoints

The efficacy and safety primary endpoints of this study will be evaluated by assessing changes from Baseline to Weeks 26 in the following:

- Visual Analog Scale of Neurological Symptoms. VAS are psychometric measuring tools intended to document the characteristics of disease-related symptom severity in individuals. The neurological symptoms included in this scale are (1) extreme fatigue (2) brain fog, (3) headache (4) sleep disturbances (5) loss of taste/smell.

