2. SUMMARY OF KEY PROTOCOL INFORMATION

2.1. Study Objective(s) and Endpoint(s)

Objectives	Endpoints	
Primary Objective	Primary Endpoint	
 To investigate the efficacy of intravenous infusions of HB-adMSCs (allogeneic) vs. Placebo in patients with Chronic Post-COVID-19 Syndrome as determined by improvements in individual symptom scores of Visual Analog Scale of Neurological Symptoms. (Time frame: Baseline to Week 26). To assess the safety of intravenous infusions of HB-adMSCs (allogeneic) vs. Placebo in patients with Chronic Post-COVID-19 Syndrome as determined by the incidence of adverse events or serious adverse events (Time frame: Baseline to Week 26). 	 The efficacy and safety primary endpoints of this study will be evaluated by assessing changes from Baseline to Weeks 26 in the following: Changes in the Visual Analog Scale of Neurological Symptoms. VAS are psychometric measuring tools intended to document the characteristics of disease-related symptom severity in individuals. The neurological symptoms included in this scale are (1) extreme fatigue (2) 3 brain fog, (3) headache (4) sleep disturbances (5) loss of taste/smell. Incidence of treatment-emergent Adverse Events (TEAEs) and serious Adverse Events (SAEs). Incidence of AEs of special interest (serious or nonserious), including thromboembolic events, infections, and hypersensitivities Changes in laboratory values, vital signs, weight, physical exam results, and medications used to treat Chronic Post-COVID-19 Syndrome. 	
Secondary Objective	Secondary Endpoint	
• To investigate the efficacy of intravenous infusions of HB-adMSCs (allogeneic) vs. Placebo in patients with Chronic Post-COVID-Syndrome as determined by	The efficacy and safety secondary endpoints of this study will be evaluated by assessing changes from Baseline to Weeks 26 in the following:	

Objectives	Endpoints

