5.1.1. General Methodology

Unless otherwise stated, all hypotheses will be tested at a 2-sided significance level of 0.05 and 95% confidence interval. All continuous measurements will be summarised descriptively at each visit by treatment using observed data.

Summary of continuous variables will be presented using N, Mean, 95% confidence interval of mean, Standard Error of mean (SE), Standard Deviation (SD), Median and Range (Minimum and Maximum). The categorical variables will be presented using number and percentage based on N.

For measurements over time mean values will be plotted to explore the trajectory over time. Observed data will be used as the basis for plotting data along with bars as +/- SE, not otherwise specified.

As a primary analysis, a standard Analysis of Covariance (ANCOVA) will be applied for primary and secondary endpoint to test the significance of the effects of the treatment at Week 26. The model includes treatment as fixed factor and the corresponding baseline value as a covariate.

A parametric Repeated Measures Analysis (RMA) Model will be applied as a secondary analysis to test the significance of the effects of the treatment at Week 2, Week 6, Week 10, Week 14, Week 20 and Week 26 including baseline as covariate.

Presentation of results from a statistical analysis model will include the estimated mean treatment effects (Least Square Means (LSMeans)). For all endpoints analysed statistically, estimated mean treatment differences will be presented together with two-sided 95% confidence intervals and p-values,

HB-adMSCs - Placebo

Pairwise t-test will be performed on the efficacy endpoints to test the difference between baseline and week 26 (EOS) as secondary analysis. Data for all the efficacy outcomes will be checked for normality (Shapiro-Wilk Test).

When there is a larger deviation of data distribution from normality, appropriate nonparametric test will be used.

Study population analyses including analyses of subject disposition, demographic and baseline characteristics, medical history, prior and concomitant medications.

Disposition summary includes, subject screened, randomized and disposition at end of study – Week 26 along with reasons for withdrawals. Subjects in different analysis populations also will be presented.

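### The primary safety objective compares adverse-event incidence with placebo, but the SAP text specifies no between-arm estimate or interval for it

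*SAP*

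**What the plan says.** SAP section 2.1 repeats the protocol's second primary objective: "To assess the safety of intravenous infusions of HB-adMSCs (allogeneic) vs. Placebo", "as determined by the incidence of adverse events or serious adverse events (Time frame: Baseline to Week 26"). The first safety item in its primary endpoint column is "Incidence of treatment-emergent Adverse Events (TEAEs) and serious Adverse Events (SAEs"), followed by the incidence of special-interest AEs (thromboembolic events, infections, hypersensitivities).

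The method is in SAP section 5.3.2.2: "Treatment Adverse events (TAES) are summarised descriptively, whereas non-TEAEs are presented in listings". On the statistics it says "TAE data will be displayed in terms of the number of subjects with at least one event (N"), together with the "percentage of subjects with at least one event (%) and the number of events (E"). Overview tables and tables by system organ class and preferred term follow. One sentence says that both the incidence and the risk of special-interest AEs will be summarised, without saying how risk is estimated. Details of the displays are left to a programming specification.

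SAP section 5.1.1 gives categorical variables a number and a percentage. Its rule on intervals reads "For all endpoints analysed statistically, estimated mean treatment differences will be presented together with two-sided 95% confidence intervals", which concerns differences in means. The hypotheses in SAP section 3 concern efficacy only.

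**The concern.** The objective is comparative, placebo-controlled and primary, yet the output specified for it contains no comparison. The efficacy endpoints get a treatment difference with a 95% interval. AE and SAE incidence gets a count, a percentage and an event total. Section 5.3.2.2 does not even say that these are shown by treatment group; that has to be inferred from the definition of the safety analysis set.

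At stake is how the primary safety result can be read. In a trial of 80, the events that matter most (SAEs and thromboembolic events) may number zero or a handful. Without an interval, the tables do not show how large an excess on HB-adMSCs the data leave open. The documents give no event rate, power or safety margin that would tell the reader this in another way. If the interval is added only after unblinding, the event groupings and the method are also chosen after unblinding.

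**Working it through.** **Inputs**
- Total sample size 80, with no derivation given (SAP section 6). It cannot be reproduced, because the documents state no effect size, event rate, power or dropout.
- Allocation 1:1 (SAP section 2.2), so 80/2 = 40 per arm. The actual size of the safety set is unknown; 40 per arm is an assumption, and 32 per arm is used as a sensitivity value.
- Two-sided 95% confidence (SAP section 5.1.1), z = 1.96.
- The event counts below are illustrations. The documents give none.

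**Step 1: one arm with no events.** The exact two-sided 95% upper limit solves (1 - p)^n = 0.025, so p = 1 - 0.025^(1/n).
- n = 40: 1 - 0.025^(1/40) = 1 - 0.9119 = 0.0881, or 8.8%.
- n = 32: 1 - 0.025^(1/32) = 0.1089, or 10.9%.

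Seen the other way, the chance of 0/40 is 0.95^40 = 13% when the true risk is 5%, and 0.98^40 = 45% when it is 2%.

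**Step 2: risk difference, Newcombe interval.** With p1, p2 the observed risks (HB-adMSCs, placebo), d = p1 - p2, and Wilson limits (l1, u1), (l2, u2):

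lower = d - √[(p1 - l1)² + (u2 - p2)²]; upper = d + √[(u1 - p1)² + (p2 - l2)²].

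The Wilson limits are 0 to 0.0876 for 0/40 and 0.0258 to 0.1986 for 3/40.

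- 0 vs 0: d = 0, limits ±√(0² + 0.0876²) = ±0.0876, so -8.8 to +8.8 points. (This rounds to the same figure as Step 1 but comes from a different formula.)
- 3 vs 0: d = 0.075. Lower = 0.075 - √[(0.075 - 0.0258)² + 0.0876²] = 0.075 - 0.1005 = -0.025. Upper = 0.075 + (0.1986 - 0.075) = 0.199. So +7.5 points (-2.5 to +19.9).

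The same formula gives:

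| Events, 40 per arm | Risk difference (points) | 95% interval |
|---|---|---|
| 0 vs 0 | 0.0 | -8.8 to +8.8 |
| 2 vs 2 | 0.0 | -12.1 to +12.1 |
| 3 vs 0 | +7.5 | -2.5 to +19.9 |
| 5 vs 1 | +10.0 | -2.5 to +23.8 |
| 20 vs 20 | 0.0 | -20.9 to +20.9 |

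At 32 per arm, 0 vs 0 widens to -10.7 to +10.7.

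**Step 3: which counts would enter.** The objective runs from Baseline to Week 26. The protocol's Adverse Event Reporting Period extends about 16 weeks past the last administration, and 10 + 16 = 26 weeks. SAP section 5.3.2.2 ends the treatment-emergent window on the last infusion day, about Week 10 for a participant who receives all four infusions. SAP section 7.2.2 assigns the treatment-emergent flag Y to events that start before the first dose and N to those on or after it, the reverse of section 5.3.2.2. An interval for TEAEs would inherit whichever numerator is programmed.

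**The case against.** The strongest reply is that nothing is lost. An unadjusted risk difference and its interval follow entirely from the planned counts and the arm sizes, as the working shows. Descriptive AE tables are usual in a small phase 2 trial, and the SAP is consistent with itself: it keeps intervals for endpoints analysed statistically and states hypotheses for efficacy only. The undefined risk of special-interest AEs may already mean a comparative estimate, and the programming specification may add an interval column.

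Much of this stands. A reader might infer that the trial could not produce the comparison at all; the documents do not support that, since what is missing is a specified summary and not the data. A reader might also infer that the plan treats a zero or equal count as showing safety. No section says so, and there is no safety margin or success rule. Nor is a missing hypothesis test the fault.

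What does not stand is that the gap is therefore only a display detail. The contrast and the interval method for a primary endpoint belong in the SAP. The sentence on risk defines no estimator, contrast or interval, and does not cover any TEAE or any SAE.

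**Conclusion.** The point holds as a gap in estimation. A comparative primary safety objective has no between-arm estimate or interval in the SAP text, only numbers and percentages of participants and numbers of events. At 40 per arm, a zero count leaves a true risk of up to 8.8% open, and equal counts leave differences of roughly 9 to 21 points open in either direction, depending on how common the event is. These sizes rest on an assumed 40 per arm and on illustrative counts; a smaller safety set widens them. The conclusion is limited to the SAP text, since the programming specification could not be seen. The change is worth making because it is cheap and answers the trial's own primary question. The treatment-emergent definitions need settling first, because intervals would otherwise lend precision to counts that may be wrong.

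**What to change.** In SAP section 5.3.2.2, for any TEAE, any SAE and each special-interest category:
- show n/N and percentage by treatment group;
- give the risk difference (HB-adMSCs - Placebo) with a two-sided 95% Newcombe interval, and define the risk of special-interest AEs in these terms;
- give the exact upper bound where an arm has no events;
- state that these are estimates, without hypothesis tests.

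Apply them to counts over the Baseline-to-Week-26 period named in the objective. Before that, reconcile the treatment-emergent window in section 5.3.2.2 and the reversed flag in section 7.2.2 with SAP section 2.1 and the protocol's Adverse Event Reporting Period.

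The cost is a paragraph of SAP wording, a few columns in the summary tables and the reconciliation of the two definitions. No data collection changes. The downside for the sponsor is that wide intervals make the safety statement look less favourable.

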5.3.2.3. Clinical Laboratory data

Laboratory evaluations including CBC- complete blood count, CMP- comprehensive metabolic panel and Coagulation Panel. The details of the planned displays are in programming specification document.

All laboratory parameters, including numerical urine analysis parameters will be summarised descriptively. Categorical urine analysis results will be summarized using count and percentage based on subjects.

Results of urine pregnancy test will be listed in individual subject data listings only.

Individual laboratory evaluations will be listed. In addition, a listing containing individual subject laboratory values outside the normal reference ranges will be provided.

Data recorded at unscheduled assessments will not be included in tables and figures but will be listed.

5.3.3. Additional Safety Assessments

The analyses of non-laboratory safety test results including physical examination and vital signs.

Physical Examination and Vital signs will be summarized using count and percentage based on subjects. The vital signs based on visit and change from baseline will be summarized using descriptive statistics.

Individual Vital signs, Physical Examination evaluations will be listed.

The details of the planned displays are in programming specification document.

5.4. Changes to Protocol Defined Analyses

Analysis is planned as per protocol. No deviation from the planned protocol specified analysis.

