Suppose an infusion is stopped for a subject due to an adverse event or serious adverse event, including but not limited to hypersensitivity reaction/anaphylaxis. In that case, no additional study treatment will be given to the study participant who develops the event. Although the study participant will not

receive the investigational product, he or she must be followed for safety purposes according to the protocol.

Study Stopping Rules

This Clinical Trial will stop if any of the following events are present:

1. Subject's Death.
2. Any thromboembolic event will cause a pause in the study until an evaluation can be done by the DSMB, Principal Investigator and Medical Monitor to determine relationship.
3. Any cerebrovascular ischemia or seizure event occurring within 72 hours after any of the investigational product administrations.
4. Any Serious Adverse Events of the following:
 - When there is one CTCAE.v5 grade 4 or 5 AE, irrespective of attribution.
 - Either any CTCAE Grade 2 adverse event that persists for more than two weeks or any Grade 3 adverse event that occurs within 72 hours after product administration.

Should the study participant discontinue study treatment, he/she will be followed for safety according to the protocol safety monitoring plan. The study participant will receive follow-up communication via phone calls or electronically to ascertain the outcome until resolved fully. All will be documented as per protocol.

FDA shall review all changes to the study-stopping rules. If the study is suspended for any reason, it will not be re-opened until FDA agrees. Whether the study is stopped or suspended, all subjects will be followed to the EOS visit.

Statistical Methods

The sample size consists of 80 subjects who have been diagnosed with Chronic Post-COVID-19 Syndrome. All data collected from subjects who are enrolled and received the investigational product will be analyzed. The incidence of Adverse Events and Serious Adverse Events will be recorded and reported. Efficacy will be measured by improving the subject's signs and symptoms associated with Chronic Post-COVID-19 Syndrome. Interim analysis of all safety and efficacy data may be performed at any time deemed appropriate by the Sponsor. Data may be analyzed for internal informational purposes, reports, presentations, and manuscripts.

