A repeated measure mixed model will be used to assess within-subject changes from baseline. Correction for multiple comparisons will be employed for post-hoc comparisons. Chronic Post COVID-19 Syndrome's assessments (VAS, FAS, PHQ-9, and SF-36) at infusion 1 (before treatment) will be utilized as a baseline.

Data Handling

Case Report Forms (CRF)

As used in this protocol, the term CRF should be understood to refer to either a paper form or an electronic data record, or both. Reports received by the site, or the central laboratory should be printed, retained as source documentation, and signed by the principal investigator, indicating which values are considered clinically significant and reported as AEs if applicable.

The completion, review, and approval of all CRFs and the completeness and authenticity of all clinical and laboratory data entered on these CRFs are always the Principal Investigator's responsibility. The signature of the Principal Investigator will be required to attest that the information contained on the CRFs is accurate.

Changes in the Conduct of the Clinical Trial

Protocol Amendments

Any change to the protocol will need to have a protocol amendment submitted to the IND, and FDA and IRB must agree before proceeding.

Premature Clinical Trial Termination

Both the Study Investigator and Sponsor have the right to terminate the clinical trial at any time. Should this become necessary, the procedures will be agreed upon after consultation between the two parties. In terminating the clinical trial, the Sponsor and the Study Investigator will ensure that adequate consideration is given to protect the best interests of the study participants. Regulatory authorities and IRB will be informed.

In addition, the Sponsor reserves the right to terminate the participation of any clinical trial site. Conditions that may warrant termination include, but are not limited to:

- Insufficient adherence to protocol requirements
- Failure to enter patients at an acceptable rate
-

Reporting and Publication

Neither the complete nor any part of the study results carried out under this protocol nor any of the information provided by the sponsor to perform the study will be published or passed on to any third party without the consent of the study sponsor.

Any investigator involved with this study is obligated to provide the sponsor with complete test results and all data derived from the study.

Archiving

Investigator File

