3.2. Interim Analysis

No interim analysis planned.

Population	Definition / Criteria	Analyses
		Evaluated
Safety analysis set	 All randomized subjects who received at least one dose of HB-adMSCs infusion or placebo. If participants receive a treatment different to their randomized treatment, they will be analysed according to the treatment actually received. 	 Safety Study Population
Efficacy analysis set	 All randomized participants who received all 4 infusions of HB-adMSCs or placebo. Participants will be analysed according to their randomized treatment. 	• Efficacy
Screened Population	 This population consists of all subjects who signed an ICF to participate in the clinical trial. This population will be used for summarizing screening failures and reasons for screening failures. 	Study Population

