5.1.2. Baseline Definitions

For all endpoints, the baseline value will be the latest pre-treatment assessment visit with a non-missing value. i.e., If an assessment has been made both at screening visit (Visit 1) and Week 0 infusion 1 visit (Visit 2, Week 0), the value from the Week 0 visit is used as the baseline value. If the value measured at the Week 0 visit is missing and the assessment also has been made at screening, then the screening value is used as the baseline value.

Unless otherwise stated, if baseline data is missing no derivation will be performed and baseline will be set to missing.

5.2. **Primary Endpoint(s) Analyses**

The primary objective of this study is to compare HB-adMSCs to Placebo on change in Visual Analog Scale of Neurological Symptoms scores. Efficacy analysis set will be used for this analysis. The details of the planned displays are in programming specification document.

5.2.1. **Definition of endpoint(s)**

Objectives	Endpoints
Primary Objective	Primary Endpoint
To investigate the efficacy of intravenous infusions of HB-adMSCs (allogeneic) vs. Placebo in patients with Chronic Post-COVID-19 Syndrome as determined by improvements in individual symptom scores of Visual Analog Scale of Neurological Symptoms. (Time frame: Baseline to Week 26).	Changes in the Visual Analog Scale of Neurological Symptoms. VAS are psychometric measuring tools intended to document the characteristics of disease-related symptom severity in individuals. The neurological symptoms included in this scale are (1) extreme fatigue (2) brain fog, (3) headache (4) sleep disturbances (5) loss of taste/smell.

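### SAP 5.4 declares no deviation from the protocol, yet the SAP limits efficacy to participants who received all four infusions and makes a Week 26 ANCOVA primary where the protocol names only a repeated-measures model

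*SAP*

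**What the plan says.** SAP Section 5.4 exists to record changes to the protocol-defined analyses. Its whole content is: "Analysis is planned as per protocol. No deviation from the planned protocol specified analysis".

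**Population.** The protocol's Statistical Methods say: "All data collected from subjects who are enrolled and received the investigational product will be analyzed". The analysis-set table belonging to SAP Section 4 defines the efficacy set as: "All randomized participants who received all 4 infusions of HB-adMSCs or placebo". SAP 5.2 assigns that set to the primary endpoint.

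**Model.** The protocol says: "A repeated measure mixed model will be used to assess within-subject changes from baseline". It names no other efficacy model. SAP 5.1.1 says: "As a primary analysis, a standard Analysis of Covariance (ANCOVA) will be applied for primary and secondary endpoint", and then: "A parametric Repeated Measures Analysis (RMA) Model will be applied as a secondary analysis". SAP 5.2.2 repeats this order for the primary endpoint.

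**Baseline.** The protocol says that the VAS, FAS, PHQ-9 and SF-36 assessments "at infusion 1 (before treatment) will be utilized as a baseline". SAP 5.1.2 follows this when a Week 0 value exists. When it is missing and a screening value exists, "then the screening value is used as the baseline value".

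**The concern.** A reader of the study report relies on the section on changes to learn whether the primary result comes from the analysis the protocol described. Here that section gives an assurance that the rest of the SAP does not bear out, and no other SAP section acknowledges or explains the differences.

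The population change matters most. Participants with one to three infusions received product and fall within the protocol's sentence, but they leave the primary efficacy comparison. Some will have stopped because of an adverse event, which treatment can affect. The comparison is then no longer between the randomised groups, and the plan tells the reader that nothing has changed.

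**Working it through.** The main check compares the two documents. The plan gives no figure to reproduce: SAP Section 6 states 80 subjects, with no effect size, SD, power or dropout rate.

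**1. Population.** The protocol sentence stands in a paragraph that covers both adverse events and efficacy, and the protocol defines no narrower efficacy set. I read its reference to investigational product as covering either arm's infusion, as the protocol's visit procedures do. The SAP's safety set needs at least one dose and its efficacy set needs all four. The two sets therefore differ by the participants with one, two or three infusions.

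The protocol's Infusion Stopping Rules say that a participant whose infusion is stopped for an adverse event receives no further study treatment but stays in safety follow-up. Anyone stopped at infusion 1, 2 or 3 therefore cannot enter the efficacy set. A stop during infusion 4 depends on whether a partial infusion counts as received, which the SAP does not say. Participants who withdraw voluntarily before infusion 4 are excluded as well.

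**2. Scale of the population change (illustration only).** Inputs from the documents are 80 subjects (SAP Section 6), 1:1 allocation (SAP 2.2), hence 80/2 = 40 per arm, and two-sided alpha 0.05 (SAP 5.1.1). I assume 80% power as a benchmark and equal exclusion in both arms, unrelated to outcome.

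- Detectable difference in SD units: (1.960 + 0.842) × √(2/n). At n = 40 this is 2.802 × 0.2236 = 0.63.
- Power for that same difference at smaller n: Φ(0.626 × √(n/2) − 1.960).

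| Assumed share per arm without all four infusions | n per arm | Detectable difference (SD) | Power for 0.63 SD |
|---|---|---|---|
| 0% | 40 | 0.63 | 80% |
| 5% | 38 | 0.64 | 78% |
| 10% | 36 | 0.66 | 76% |
| 20% | 32 | 0.70 | 71% |
| 30% | 28 | 0.75 | 65% |

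These figures ignore the precision gained from baseline adjustment and any selection bias. The 0.63 SD is what 40 per arm would detect, not a target taken from the plan.

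**3. Model.** ANCOVA appears nowhere in the protocol. The SAP puts it first for the primary endpoint and ranks the model that the protocol does name second. For the secondary endpoints the SAP disagrees with itself: 5.1.1 makes ANCOVA primary, while 5.3.1 makes the repeated-measures model primary and ANCOVA secondary. One statement of conformity cannot cover both orders.

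**4. Baseline.** The two rules agree whenever a Week 0 value exists. They differ only when it is missing, and the protocol does not address that case. The fallback can operate for the VAS, which the Schedule of Assessments (protocol Table 1) places at both screening and Week 0. It cannot operate for the SF-36, which is not scheduled at screening. SAP 7.2.4 also lets unscheduled visits count in deriving baseline. This is an extension of the protocol rule, and a small one.

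**The case against.** An SAP may refine a brief protocol, and much of this one does. The protocol labels no model primary, describes its mixed model for within-subject change and specifies no between-group test. A Week 26 ANCOVA fits the protocol's endpoint of change from baseline to Week 26, and the repeated-measures model is retained. The protocol's population sentence is general and does not claim to define an efficacy set.

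Part of this stands, and it rules out several stronger readings that a reader might infer:

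- **That the SAP replaced a designated primary analysis.** The protocol designated none. The supportable statement is that ANCOVA takes first place over the only model the protocol names.
- **That the baseline rule was replaced.** It was extended to a case on which the protocol is silent.
- **That the false-positive rate is inflated, or that the sponsor can choose between models after seeing the data.** SAP 5.1.1 and 5.2.2 both fix ANCOVA as primary for the primary endpoint. The documents show no inflation of that single test.
- **That the changes were made after unblinding.** The SAP's front matter is not available, so its date and the protocol version it follows cannot be seen.

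The objection does not rescue 5.4. A sentence saying that all data from dosed participants will be analysed cannot be squared with an efficacy analysis that omits some of them. A model absent from the protocol cannot be covered by a statement that nothing changed.

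**Conclusion.** SAP 5.4 is inaccurate in two material respects: the efficacy population, which is the more serious, and the model ranked first for the primary endpoint. The baseline fallback is a minor third item. The conclusion rests on the text of the two documents and needs no assumed figure.

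Its numerical size cannot be fixed, because the documents give no rate of incomplete dosing. Under the assumed 5% to 30%, 2 to 12 participants per arm would leave the primary comparison. The loss of power would be modest at the low end and appreciable at the high end. Any bias from selecting on completed dosing comes from the efficacy-set definition itself; the fault in 5.4 is that it conceals the selection. The correction should be made, and it does not require abandoning ANCOVA as the primary analysis.

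**What to change.** Replace the statement in SAP 5.4 with a list of the changes: restriction of efficacy to participants with all four infusions, ANCOVA as the primary model for the primary endpoint, and the screening and unscheduled-visit provisions for baseline. Give each one its reason and say when it was fixed relative to unblinding. Reconcile 5.1.1 with 5.3.1 on which model comes first for the secondary endpoints.

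Beside the primary ANCOVA result, report the Week 26 treatment contrast from the repeated-measures model already specified in SAP 5.2.2. Fit it in all randomised participants who received at least one infusion, analysed as randomised, with the infusion 1 value as baseline. Label it as the analysis closest to the protocol's description, since the protocol sets out no between-group test. Protocol Table 1 schedules the VAS after baseline at Weeks 2, 6, 10 and 26 but not at the Week 14 and 20 calls, so the model should use the four visits with data. State how many dosed participants have no post-baseline VAS and so cannot contribute.

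The cost is a rewritten paragraph and one further output from a planned model. The report must then disclose that its primary analysis differs from the protocol's description.
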